- ^f CGI interviews collected from Week 36 will be used to review all areas of the functioning section (including complex daily activities and basic functions) and will be used to determine whether there have been any changes or additions to the functioning at the Week 48 visit, with both the caregiver and participant independently. This will be used to assign the Week 48 SEADL score.

CONFIDENTIAL

The information contained herein may not be used, disclosed, or published without the written consent of Biogen MA Inc.

Table 3: Extension Period Procedural Outline

Procedure	Week 52	Weeks 56, 60, 68, 72, 80, 84, 92, 96, 104, 108, 116, 120, 128, 132, 140, 144, 152, 156, 164, 168, 176, 180, 188, and 192 ^a . (±7 days)	Weeks 64, 88, 112, 136, 160, 184 (±7 days)	Weeks 76, 100, 124, 148, 172, 196 (±7 days)	Early Discontinuation ^b	Notes
Eligibility Assessments						
Concomitant Medications	Review of concomitant medication as per Section 7.7 .					
Safety Assessments						
Physical Examination			See notes	X	X	At Week 64 only.
Targeted Physical Examination		X	X	X	X	Post-dose. Targeted, problem-focused physical examination performed at clinician's discretion (e.g., to evaluate any AEs).
Neurological Examination				See notes		Week 100 only. Besides documenting signs of PSP, the NE should focus on any clinical evidence of increased intracranial pressure (e.g., history of headache, vomiting, or visual disturbances, and neurologic signs such as pupillary abnormalities and papilledema) that might contraindicate a lumbar puncture.
Physical Measurements			X	X	X	Weight only.
Vital Signs		X	X	X	X	

CONFIDENTIAL

The information contained herein may not be used, disclosed, or published without the written consent of Biogen MA Inc.

Procedure	Week 52	Weeks 56, 60, 68, 72, 80, 84, 92, 96, 104, 108, 116, 120, 128, 132, 140, 144, 152, 156, 164, 168, 176, 180, 188, and 192 ^a . (±7 days)	Weeks 64, 88, 112, 136, 160, 184 (±7 days)	Weeks 76, 100, 124, 148, 172, 196 (±7 days)	Early Discontinuation ^b	Notes
12-Lead Electrocardiogram (ECG)				X	X	
Assess Infusion site		X	X	X	X	
Laboratory Tests			See notes	X	X	At Week 64 only.
Pregnancy Test		X	X	X	X	For WOCBP only (serum or urine - local/site).
			■	■	■	
Immunogenicity Assessments						
Serum Anti-BIIB092 Antibody ^c				X		Additional event driven samples may be justified; see Section 14.
Adverse Event Reporting						

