14. IMMUNOGENICITY ASSESSMENTS

A validated immunoassay will be used to assay samples for the presence of, and measure titers of, anti-BIIB092 antibodies in serum on an ongoing basis in Study 251PP301. Samples will be collected during the 52-week double-blind period at Day 1, Week 4, Week 8, Week 12, Week 24, Week 36, and Week 48 (Table 2). In addition, samples will also be collected during the open-label extension period approximately every 24 weeks (Table 3). All samples will be collected predose.

Anti-drug antibody (ADA) titers will be monitored throughout the course of Study 251PP301. If ADAs are observed, analyses will be conducted to assess impacts on safety, pharmacological, and efficacy measures across treated participants with and without ADAs. ADAs may also be assessed for neutralizing activity.

Participants who withdraw from Study 251PP301 with ADA titers that are not stable or are increasing in two consecutive samples leading up to discontinuation will be asked to return for follow-up assessment approximately every 6 weeks for up to 24 weeks for measurement of ADAs and immunological AE assessment until resolved (defined as two sequential samples showing no change or declining levels).

Clinically relevant immune reactions (e.g., hypersensitivity reactions) will be treated according to current standard of care medical practice. Additional samples for immunogenicity assessments referred to as “event driven” samples may be justified on the basis of \geq Grade 3 hypersensitivity reactions. The immunogenicity and corresponding drug exposure (PK) data from these samples will be reported as part of a participant’s overall PK and immunogenicity assessment.

CONFIDENTIAL

The information contained herein may not be used, disclosed, or published without the written consent of
Biogen MA Inc.

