6.2.4 Adverse event of special interest

Immunogenicity is an AESI in the BIIB092 clinical development program. Adverse events representing potential immune/hypersensitivity reactions will be identified using customized MedDRA search criteria: Anaphylactic reaction, Angioedema, and Severe cutaneous adverse reactions via SMQ (narrow and broad) search; Eosinophilia, and Miscellaneous terms. Further details are given in Appendix 11.1.

An incidence proportion table for potential immune/hypersensitivity reactions organized by SMQ/Miscellaneous categories and by PT (for both AEs and SAEs), and similarly for potential immune/hypersensitivity reactions for subjects with and without treatment emergent positive anti-drug antibody (ADA) results will be presented for both AEs and SAEs for the OLE Period. Positive treatment emergent ADA will be based on the definition in Section 8 using the integrated placebo-controlled and open label extension data.

An exposure adjusted incident rate table will be provided for the active treatment (placebo-controlled and OLE) period.

The following analyses (incidence proportion only) will be performed for the OLE period to explore the relationship between ADAs and the safety of BIIB092:

- AEs for subjects with and without positive treatment emergent ADAs
- SAEs for subjects with and without positive treatment emergent ADAs

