6.2.5 Infusion reactions

Infusion reactions will be identified through 1) temporal association, defined as those events which occur on the day of an infusion or the subsequent two calendar days after an infusion; and 2) through a custom MedDRA search of preferred terms. The list of custom MedDRA search terms can be found in Appendix 11.2. A serious infusion reaction is a serious adverse event which is identified by one or both methods.

For the OLE period, an overall summary of infusion reactions will be provided with the number of subjects (n, %) with any infusion reaction; with any infusion reaction identified by temporal association only; with any infusion reaction identified through the custom search only; and any infusion reaction identified through both methods. Additionally, the following incidence proportion tables will be provided for the OLE period:

1. Infusion reactions (temporal association or custom search) by SOC and PT
2. Serious infusion reactions (temporal association or custom search) by SOC and PT
3. Infusion reactions (temporal association or custom search) for subjects with and without positive treatment emergent ADAs by PT
4. Serious infusion reactions (temporal association or custom search) for subjects with and without positive treatment emergent ADAs by PT
5. Infusion reactions that occurred in temporal association to an infusion by physical location of infusion (in-clinic vs. home) by SOC and PT
6. Serious infusion reactions that occurred in temporal association to an infusion by physical location of infusion (in-clinic vs. home) by SOC and PT
7. Infusion reactions identified through custom search criteria by PT
8. Infusion reactions (temporal association or custom search) by 12-week intervals by PT

Positive treatment emergent ADA will be based on the definition in Section 8 using the integrated placebo-controlled and open label extension data.

An exposure adjusted incident rate table for infusion reactions will be provided for the active treatment (placebo-controlled and OLE) period.

Additionally, the following incidence proportion tables will be provided for the active treatment (placebo-controlled and OLE) period:

1. Infusion reactions that occurred in temporal association to an infusion by physical location of infusion (in-clinic vs. home) by SOC and PT
2. Serious infusion reactions that occurred in temporal association to an infusion by physical location of infusion (in-clinic vs. home) by SOC and PT

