6.2.3 Adverse event of special interest

Immunogenicity is an AESI in the BIIB092 clinical development program. Adverse events representing potential immune/hypersensitivity reactions will be identified using customized MedDRA search criteria: Anaphylactic reaction, Angioedema, and Severe cutaneous adverse reactions via SMQ (narrow and broad) search; Eosinophilia, and Miscellaneous terms. Further details are given in Appendix 11.3.

An incidence proportion table for potential immune/hypersensitivity reactions organized by SMQ/Miscellaneous categories and by PT (for both AEs and SAEs), and similarly for potential immune/hypersensitivity reactions for subjects with and without treatment emergent positive anti-drug antibody (ADA) results (as defined in Section 8) will be presented for both AEs and SAEs. A listing of potential immune/hypersensitivity reactions will be provided.

The following analyses (incidence proportion only) will be performed to explore the relationship between ADAs and the safety of BIIB092:

- AEs for subjects with and without treatment emergent positive ADAs
- SAEs for subjects with and without treatment emergent positive ADAs

In this study, additional samples for ADA, referred to as “event driven” samples, may be collected for subjects with hypersensitivity events. A listing of AEs for subjects with any event driven ADA samples will be provided.

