In this study, additional samples for ADA, referred to as “event driven” samples, may be collected for subjects with hypersensitivity events. ADA data will be listed for subjects with any event driven sample. Data from these samples will be considered part of a subject’s overall ADA assessment.

The analysis windows are defined based on the scheduled post-baseline visits for ADA in Table 13. The same visit windowing approach described in Section 6.1.2 will be used.

Table 13 Visit Windows for Anti-drug Antibody

| Analysis visit | Target visit day | Analysis visit window |
|-----------------------|-------------------------|--|
| Baseline | 1 | Last available value prior to the first dose of study drug |
| Week 4 | 29 | [1 (post-dose only), 42] |
| Week 8 | 57 | [43, 70] |

| | | |
|---------|-----|--|
| Week 12 | 85 | [71, 126] |
| Week 24 | 169 | [127, 210] |
| Week 36 | 253 | [211, 294] |
| Week 48 | 337 | [295, the end day of the placebo-controlled period*] |

[figure not shown]
* The end day of the placebo-controlled period is the last day before the first dose in OLE for subjects who enter OLE, and is the last day in study for subjects who do not enter OLE.

[figure not shown]

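### The ADA-by-adverse-event tables use ever-positive status that includes reaction-triggered samples and ignores time order, so they can be biased in either direction, most of all for late starters in the extension

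*SAP*

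**What the plan says.** **Event-driven samples.** Protocol Section 14 allows extra immunogenicity samples: these "samples may be justified on the basis of" reactions of at least the severity given as "Grade 3 hypersensitivity reactions". It has the results reported within the participant's overall PK and immunogenicity assessment. Section 8 of each SAP states a wider trigger, saying only that event-driven "samples, may be collected for subjects with hypersensitivity events", and pools the results with the scheduled ones ("Data from these samples will be considered part of a" subject's overall ADA assessment).

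**Classification.** In Section 8 of each SAP, one qualifying post-baseline positive sample makes the subject treatment-emergent positive. AE onset plays no part in the definition.

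**Tables.** Placebo-controlled SAP 6.2.3 plans "AEs for subjects with and without treatment emergent positive ADAs", and the same split for SAEs and for potential immune/hypersensitivity reactions. All are incidence proportions. OLE SAP 6.2.4 repeats these for OLE events: "Positive treatment emergent ADA will be based on the definition in Section 8 using the integrated placebo-controlled and open label extension data". OLE SAP 6.2.5 adds "Infusion reactions (temporal association or custom search) for subjects with and without positive treatment emergent ADAs by PT" and a serious-reaction counterpart. The placebo-controlled SAP has no infusion-reaction table by ADA status (its 6.2.4).

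**Schedule.** Protocol Section 14 gives double-blind samples at Day 1 and Weeks 4, 8, 12, 24, 36 and 48. Table 2 marks none at Week 52 or Early Discontinuation. In Table 3 the row "Serum Anti-BIIB092 Antibody" is marked only for Weeks 76, 100 and every 24 weeks after that.

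**The concern.** Two features interact. First, the outcome can trigger the exposure measurement: a hypersensitivity reaction may add a sample, and one positive sample is enough for the label. Second, status is fixed over the whole period, so an event that precedes the first positive sample still counts in the ADA-positive column.

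Both SAPs name immunogenicity as the adverse event of special interest, and these are the tables a reader will use to judge whether ADA carries a safety risk. They could suggest a link that is absent, or weaken or reverse one that is real. Late starters are the most exposed. They first receive BIIB092 at Week 52 and have no scheduled ADA sample until Week 76, whereas early starters have three by Week 12. The OLE SAP (5.3) also says that too few patients will have reached Week 100 at its database lock, so many late starters will have at most one scheduled sample on BIIB092.

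**Working it through.** The documents give no ADA incidence, reaction rate or ADA-AE association, so there is no planned figure to reproduce. The check asks what the tables show when ADA and reactions are truly independent.

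**Inputs from the documents:** six scheduled post-baseline samples (Protocol 14); 306 participants on BIIB092 and 25% dropout (Protocol 17.1); OLE samples about every 24 weeks (Protocol 14).

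**Assumed:** per-sample transient positivity q of 0.5% to 5%, or persistent ADA in 5% to 20% by Week 48; a reaction rate e of 5% (30% as a variant); an event-driven sample after 0%, 20% or 100% of reactions; no further scheduled samples after 0% or 50% of reactions.

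**1. Closed form, transient ADA, complete follow-up, every reaction sampled.**
- P(positive | no reaction): b = 1 − (1 − q)^6. P(positive | reaction): a = 1 − (1 − q)^7.
- P(reaction | positive) = e·a / [e·a + (1 − e)·b]. P(reaction | negative) is the same with 1 − a and 1 − b.
- At q = 2%: b = 0.1142 and a = 0.1319, giving 0.0573 and 0.0490, a relative risk (RR) of 1.17.
- For q from 0.5% to 5% the RR is 1.16 to 1.19.
- If 20% of reactions are sampled, replace a with b + 0.2(a − b): the RR is 1.03 to 1.04.

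**2. Simulation on the Week 4/8/12/24/36/48 schedule** (3,000,000 subjects, e = 5%, no true link):

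| Event-driven sampling | ADA type | After a reaction | Dropout | RR |
|---|---|---|---|---|
| Every reaction | Transient | Sampling continues | 0% | 1.14–1.18 |
| Every reaction | Transient | Sampling continues | 25% | 1.22–1.25 |
| Every reaction | Persistent | Sampling continues | 0% | 1.00–1.01 |
| Every reaction | Persistent | Sampling continues | 25% | 1.09–1.10 |
| Every reaction | Transient | Half stop | 0% or 25% | 0.93–1.00 |
| Every reaction | Persistent | Half stop | 0% or 25% | 0.73–0.82 |
| None (scheduled only) | Either | Sampling continues | 0% | 0.99–1.01 |
| None (scheduled only) | Either | Sampling continues | 25% | 1.04–1.11 |
| None (scheduled only) | Either | Half stop | 0% or 25% | 0.70–0.88 |

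Persistent ADA with dropout gives much the same RR with or without event-driven samples (1.09–1.10 against 1.09–1.11). That part comes from unequal follow-up in a crude proportion.

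**3. Time order.** With every reaction sampled, 41% to 60% of reactions in the ADA-positive column fell at or before the first positive sample.

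**4. Chance of a nominal positive link** (Fisher test, one-sided 0.025, n = 306, 25% dropout): 0.5% to 2.6% at a 5% reaction rate, and at most 6.8% at 30%.

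**5. Late starter with one scheduled sample, q = 2%.** The chance of a positive label is 2.0% without an event-driven sample and 1 − 0.98² = 3.96% with one. The formula in step 1 then gives 0.0944 / 0.0490, an RR of about 1.9.

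**The case against.** A reader might infer that these tables will show an ADA-hypersensitivity link even when none exists. The documents do not support that.

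- Event-driven sampling is optional, and the protocol ties it to severe reactions. If few reactions are sampled, the null RR is about 1.03 to 1.04.
- Persistent antibody is found by later scheduled samples anyway, so with complete follow-up the extra sample adds almost nothing.
- If reactors stop giving samples, the tables lean towards no link or an inverse one.
- Ignoring time order does not by itself create an association when follow-up is equal (RR about 1.00). It misattributes events and would dilute a real effect.

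It is equally tempting to say that both SAPs compare infusion reactions by ADA status. Only the OLE SAP does.

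The tables are also exploratory and carry no test. The placebo-controlled SAP lists all ADA data, the immune/hypersensitivity reactions, and the AEs of anyone with an event-driven sample. Its listings generally extend to the OLE, so time order can be traced subject by subject. The OLE SAP shows early and late starters separately.

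All of this stands, and it limits the size and certainty of the bias. It does not remove it: a listing does not correct a summary table, and showing late starters separately does not supply the missing samples.

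There is also a fair objection to simply replacing the classification. Protocol 14 wants event-driven results in the overall assessment. The first positive sample is not the date of seroconversion, so a strict onset-after-detection rule would score a genuine ADA-driven reaction as ADA-negative whenever the sample is drawn because of it. This is why the remedy below adds tables and replaces none.

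**Conclusion.** The concern holds as a possible bias of uncertain direction. In the double-blind period the null RR runs from about 0.7 to 1.25 across the assumed scenarios. It reaches about 1.9 only for a late starter with a single scheduled sample whose reaction also triggers one. Every rate behind these figures is an assumption; the documents fix only the schedule, the arm size, the dropout rate and the classification rule. The OLE tables for late starters deserve the most attention. Separately, the trigger for event-driven samples differs between Protocol 14 (Grade 3 or higher) and the SAPs (hypersensitivity events with no grade), and the passages must be reconciled, because the size of the bias depends on how many reactions are sampled.

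**What to change.** Keep event-driven results in overall ADA incidence, as Protocol 14 requires, and make these additions:

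1. For each ADA-by-AE table (placebo-controlled SAP 6.2.3; OLE SAP 6.2.4 and 6.2.5), add a companion with ADA status from scheduled samples only. On its own this is not enough: step 2 of the working leaves 1.04 to 1.11 with dropout, or 0.70 to 0.88 if half of reactors stop.
2. Add a second companion that splits AEs in ADA-positive subjects into onset before, and onset on or after, the first positive sample, with time at risk. Show reactions with a positive event-driven sample in their own row so that they are not scored as ADA-negative. OLE SAP 6.1.4 already defines an exposure-adjusted rate, but it needs a time-varying ADA split. The placebo-controlled SAP (6.1.3) defines only a follow-up-adjusted rate and would need the definition added.
3. Add an ADA tube at Weeks 56 and 64, at least for late starters, at the existing PK draw (Week 56) and safety-laboratory draw (Week 64).
4. State one trigger for event-driven samples in the protocol and both SAPs.

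Items 1 and 2 cost SAP text, extra programming and some sparse cells. Item 3 needs a protocol amendment and a small assay budget, and helps only participants who have not yet passed those visits.

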9 SAMPLE SIZE CONSIDERATIONS

Approximately 459 male and female participants will be enrolled in this study. Approximately 459 participants will be randomly assigned, in 2:1 ratio, to receive 2000 mg of BIIB092 or placebo (306 participants active and 153 placebo) administered by IV approximately once Q4W. Randomization will be stratified by country and screening Color Trails Test Part 2 score of either \leq to 170 seconds, or \geq 170 seconds. Anticipating a dropout rate of approximately 25%, approximately 345 participants (230 participants in the BIIB092 treatment group and 115 participants in the placebo group) are expected to complete the study through Week 52.

[Redacted text block containing multiple lines of obscured information]

11 APPENDIX

11.2 Implementation of the Copy Increment from Reference, Jump to Reference and Pattern Mixture Model

11.2.1 Copy Increment from Reference (CIR)

The dataset will first be imputed to monotone missing using PROC MI with the MCMC and impute=monotone option. Imputation will be carried out 1000 times and any internal missing observations, including missing baseline covariates and intermediate missing in the response variable will be replaced with the average across all imputations.

For the resulted data with monotone missing, the following steps will be used to create imputed datasets:

- (1) Data from all subjects will be used to fit a multivariate normal distribution with unstructured mean and unstructured variance using a Bayesian approach with a noninformative prior for the mean and a conjugate prior for the variance covariance matrix.
- (2) Draw a pseudo-independent sample for the linear predictor parameters and the covariance parameters from the joint posterior distribution obtained in step (1). Both steps (1) and (2) will be done using PROC MCMC in SAS.
- (3) Use the linear predictor parameters and the covariance parameters obtained in step (2) to construct new mean vectors separately for each treatment group (placebo and BIIB092). Specifically, the newly constructed mean vector for someone on treatment group T whose last observed visit was visit k is calculated as

$$\mu_T^{(k)} = \begin{cases} \mu_{i,T}, & \text{if } i \leq k \\ \mu_{k,T} - \mu_{k,P} + \mu_{i,P}, & \text{if } i > k \end{cases}$$

Here P represents the placebo group. For subjects with no post-baseline records, or subjects on the placebo group, the newly constructed mean vector is the same as the placebo mean.

- (4) Using $\mu_T^{(k)}$ from step (3) and covariance parameters from step (2), find the conditional normal distribution of the visit with missing data, and use this conditional distribution to impute the missing data.

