17. STATISTICAL CONSIDERATIONS

17.1. Sample Size Determination

Approximately 459 participants will be randomly assigned in a 2:1 ratio to receive BIIB092 or placebo (306 participants in the BIIB092 treatment group and 153 in the placebo group). Anticipating a dropout rate of approximately 25% (based on previous clinical studies in participants with PSP), approximately 345 participants (230 participants in the BIIB092 treatment group and 115 participants in the placebo group) are expected to complete the study through Week 52.

Using a two-sided, two-sample t-test with an alpha level set at 0.05, this sample size will provide 80% power to detect a difference of 3.2 points in the change in PSPRS total score from baseline to Week 52 for BIIB092 relative to placebo, assuming a common standard deviation of 9.95 [Stamelou 2016] in the change in PSPRS total score from baseline to Week 52.

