5.2.4.5 Pattern mixture model

The pattern mixture model (PMM) represents a general and flexible framework to model the predictive distribution of missing data conditional on the observed data [Little 1993, 1994]. It allows formulating assumptions regarding missing data in a transparent and clinically interpretable manner.

In the PMM framework, subjects are grouped into missing patterns so that subjects in the same pattern share similar missingness characteristics. In this analysis, missing patterns will be defined according to the reasons for early withdrawal from study as reported on the electronic case report form (eCRF). The following two patterns will be considered:

- Subjects who withdraw due to reasons that may be related to efficacy, including lack of efficacy, subject request to discontinue study treatment, subject withdrew consent, poor/non-compliance, death and withdrawal by caregiver;
- Subjects who withdraw due to reasons that are unlikely related to efficacy, including adverse event, lost to follow-up, pregnancy, subject no longer meets study criteria, administrative reason by sponsor, and other.

Subjects who withdraw due to reasons that may be related to efficacy will be penalized and their missing data will be imputed using the copy increment from reference (CIR) method [Carpenter et al. 2013] (see Section 5.2.4.1 for description of the CIR method). Subjects who withdraw due to reasons that are unlikely related to efficacy will be handled using the missing-at-random assumption and their missing data will be imputed using the standard multiple imputation method [Rubin 1987]. Subjects with missing data due to reasons other than early withdrawal (such as item missing, out of window, etc.) will be handled using the missing-at-random assumption. For both imputation methods, the following covariates will be included in the imputation model: treatment group, baseline PSPRS, baseline Color Trails 2 test (≤ 170 or > 170 seconds), region and observed post baseline PSPRS total score (data from each visit as a covariate). Implementation details can be found in Section 11.2.3.

The imputed datasets will be analyzed by MMRM model described in Section 5.1. The analyzed results from the imputed datasets will be combined based on Rubin's rules [Rubin 1987] assuming that the statistics estimated from each imputed dataset are normally distributed.

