If intermediate missing values are encountered (such as data missing at Week 12 but are available at subsequent visits), a Markov chain Monte Carlo (MCMC) method that assumes multivariate normality will be used to impute the intermediate missing values and produce a monotone missing pattern (data with only terminal missing and no intermediate missing) [Li 1988; Schafer 1997].

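### Averaging the first-stage draws in the CIR, J2R and pattern-mixture analyses discards imputation uncertainty and slightly understates standard errors at Weeks 12 to 48; Week 52 is essentially unchanged

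*SAP*

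**What the plan says.** The same preparatory step appears in placebo-controlled SAP 11.2.1 (CIR), 11.2.2 (J2R) and 11.2.3 (pattern mixture). PROC MI fills internal gaps by MCMC, 1000 times, and each gap "will be replaced with the average across all imputations". The rule covers intermediate response values and missing baseline covariates. The second stage starts from the resulting monotone data. For CIR and J2R it draws parameters from a posterior and then draws post-withdrawal values from a conditional normal distribution. For pattern mixture it uses CIR for one pattern and monotone regression for another.

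The main text is less specific. SAP 5.2.4.5 says that an MCMC method "will be used to impute the intermediate missing values and produce a monotone missing pattern" and does not mention averaging; it refers the reader to 11.2.3 for implementation. On pooling, 5.2.4.5 says "The analyzed results from the imputed datasets will be combined based on" Rubin's rules. Sections 5.2.4.1 (CIR) and 5.2.4.2 (J2R) say only that the MMRM is applied after imputation. The figure of 1000 belongs to the first stage; these sections give no number for the final imputed data sets.

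**The concern.** The average of many draws is close to a conditional mean. Putting it in the gap has two effects. It removes the residual scatter a real observation would have, so the variance at that visit shrinks. It also makes the value identical in every final data set, so the between-imputation component of Rubin's rules is zero for it. Post-withdrawal values are drawn properly, so uncertainty is kept for terminal gaps and dropped for internal ones, and the SAP gives no reason for the difference.

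Internal gaps should be expected. Protocol 5.1.5 and footnote d of Table 2 encourage withdrawn participants to return at Week 52, and a returner has gaps at the visits in between. SAP 5.2.4.5 itself anticipates missing items and out-of-window visits. The affected output is the confidence intervals and p-values at intermediate visits for both PSPRS versions and, through the pattern-mixture analysis in 5.3.1.5, for the key secondary endpoints.

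**Working it through.** **1. The plan's own figure.** Protocol 17.1 states: "Using a two-sided, two-sample t-test with an alpha level set at 0.05"; "80% power to detect a difference of 3.2 points"; "assuming a common standard deviation of 9.95"; "306 participants in the BIIB092 treatment group and 153 in the placebo group"; "Anticipating a dropout rate of approximately 25"%. Expected completers are 230 and 115.

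- SE = 9.95 × √(1/230 + 1/115) = 1.136, and 3.2/1.136 = 2.816.
- Power = Φ(2.816 − 1.960) = Φ(0.856) = 80.4% (80.2% by noncentral t).
- 345/0.75 = 460, against 459 planned.

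The stated 80% reproduces. The documents give no standard error for the CIR, J2R or pattern-mixture analyses, so there is no such figure to reproduce.

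**2. Tracing one value.** Take a participant seen at Weeks 12, 36, 48 and 52 but not at Week 24. The Week 24 value receives 1000 draws, is replaced by their mean, enters the second stage as data and is the same in every final data set. A missing Week 52 value is different. It is the last visit of the period, so the gap is always terminal and is drawn in the second stage.

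**3. Closed form for one visit.** Let m be the share of values internally missing and R² the share of variance explained by the other visits.

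- Averaging: the filled-in variance is proportional to 1 − m(1 − R²).
- Proper imputation: the variance of the mean is proportional to 1 + m(1 − R²)/(1 − m).
- SE ratio (averaged/proper) = √{[1 − m(1 − R²)] / [1 + m(1 − R²)/(1 − m)]}.

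For m = 0.10 and R² = 0.50: √(0.95/1.0556) = 0.949. For m = 0.02 and R² = 0.85: √(0.997/1.0031) = 0.997. Assumed values of m from 2 to 10% and R² from 0.50 to 0.85 therefore give 0.949 to 0.997.

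**4. Simulation of the SAP's steps.** Taken from the documents: 306 and 153 participants, five visits, 25% dropout, SD 9.95 and placebo progression of 11.24 points a year (Protocol 17.3). Assumed: intermittent missingness of 2, 5 or 10% per visit at Weeks 12 to 48, and a one-year correlation of 0.55 or 0.25. Each of eight settings had 150 replicates and 20 second-stage imputations pooled by Rubin's rules. An average of 60 draws stood in for 1000. Baseline, region and Color Trails covariates were left out, and pattern mixture was not run separately. The table gives the SE with averaging divided by the SE when each draw is carried forward, as the range over CIR/J2R and correlation settings (the 2% row is one CIR setting).

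| Intermittent missing per visit | Wk 12 | Wk 24 | Wk 36 | Wk 48 | Wk 52 |
|---|---|---|---|---|---|
| 2% | 0.996 | 0.999 | 1.003 | 1.001 | 1.003 |
| 5% | 0.979–0.989 | 0.986–0.994 | 0.990–0.999 | 0.995–1.003 | 0.999–1.006 |
| 10% | 0.953–0.976 | 0.967–0.988 | 0.972–0.989 | 0.980–0.995 | 0.996–1.001 |

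Ratios slightly above 1 are simulation noise.

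**5. Returners at Week 52.** If an assumed 40% of dropouts return, up to 0.25 × 0.40 = 10% of participants acquire internal gaps at the later visits, on top of the sporadic ones. A separate small simulation with 5% sporadic missingness then put the understatement at Weeks 12 to 48 as high as about 3 to 4%, again with no detectable change at Week 52.

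**The case against.** The strongest reply is that no planned conclusion depends on the affected numbers. The estimand in SAP 5.2.3 is at Week 52, and so are the forest plots for the sensitivity analyses. The slope and divergence analyses (5.2.5.6, 5.2.5.7) use their own or the primary MMRM, not these imputed data. This stands, and it keeps the point small. A reader might infer that the Week 52 sensitivity result is compromised; the SAP's second stage draws missing Week 52 values properly, and the simulations show no detectable change there.

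A reader might also infer that the intervals are too narrow in absolute terms. That is not shown. With averaging, the Rubin SEs for CIR and J2R at Weeks 36 to 52 still exceeded the empirical SD of the estimate (J2R at Week 52: 1.07 against 0.77). The comparison here is only with carrying each draw forward.

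Nor do the documents support a large effect. With R² = 0 the formula reduces to 1 − m, so a 10% understatement at 10% missing would need unrelated visits, which is implausible for repeated scores on one scale. The contiguous 84-day windows at Weeks 12 to 36 (SAP 5.1.1) also limit gaps.

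Averaged baseline covariates could in principle reach Week 52. However, PSPRS and the Color Trails Test are both done at screening and Day 1, so missing baselines should be rare; this was not simulated.

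Finally, 11.2.3 can be read as elaborating 5.2.4.5 rather than contradicting it. That is fair, but it does not make the averaging proper multiple imputation.

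**Conclusion.** The point holds as a limited technical fault. One average replaces the draws in all three methods, is treated as observed, and takes with it the imputation uncertainty of the internal gaps. Standard errors at Weeks 12 to 48 are then slightly too small relative to proper multiple imputation: about 0 to 2% with 5% intermittent missing per visit, about 0.5 to 5% with 10%, and up to about 3 to 4% with 5% missing and 40% of dropouts returning. All these sizes rest on assumed missing rates and correlations. For pattern mixture, including the key secondary endpoints, the mechanism follows from the text but the size was not simulated. The Week 52 standard error is essentially unchanged, so this is a low-priority correction.

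**What to change.** Delete the averaging sentence in SAP 11.2.1, 11.2.2 and 11.2.3. Generate a stated, moderate number of monotone-completed PROC MI data sets (for example 100, rather than 1000). Carry each into its own second-stage imputation with its own parameter draw, analyse each with the MMRM, and pool by Rubin's rules. State the pooling rule in 5.2.4.1 and 5.2.4.2, as 5.2.4.5 already does, and state the number of final data sets for all three methods.

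The cost is SAP wording, programming, somewhat more computing because the second stage runs once per first-stage data set, and slightly wider intervals at Weeks 12 to 48. No new data are needed and the primary analysis is untouched.
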